A total of approximately 666 Subjects with T1DM are planned to be screened, approximately 506 Subjects to enter the run-in period, of which 450 are expected to enter randomised treatment.

Protocol Date: 04 February 2016 Novo Nordisk
Trial ID: NN1218-3854 Version: 4.0

Final

14 of 149

 Trial ID: NN1218-3854
 Version:

 UTN: U1111-1118-2480
 Status:

 EudraCT no.: 2010-024054-11
 Page:

Key inclusion criteria

- Male or female, age \geq 18 years at the time of signing the informed consent
- Diagnosed with T1DM ≥ 1 year prior to the day of screening
- Using the same Medtronic pump (Minimed 530G (551/751), Paradigm Veo (554/754), Paradigm Revel (523/723), Paradigm (522/722)) for CSII in a basal-bolus regimen with a rapid acting insulin analogue for at least six months prior to screening and willing to stay on the same pump model throughout the trial (if the model is changed the change should not exceed 7 consecutive days.)
- HbA_{1c} 7.0-9.0% (53-75 mmol/mol) as assessed by central laboratory at screening
- Body mass index (BMI) $\leq 35.0 \text{ kg/m}^2$ at screening
- Ability and willingness to take at least 3 daily meal-time insulin bolus infusions every day throughout the trial

Key exclusion criteria

- Any of the following: myocardial infarction, stroke, hospitalization for unstable angina or transient ischaemic attack within the past 180 days prior to the day of screening
- Planned coronary, carotid or peripheral artery revascularisation known on the day of screening
- History of hospitalization for ketoacidosis ≤180 days prior to the day of screening
- Treatment with any medication for the indication of diabetes or obesity other than stated in the inclusion criteria in a period of 90 days before screening
- Any condition which, in the opinion of the Investigator, might jeopardise a Subject's safety or compliance with the protocol

Key efficacy assessments

- HbA_{1c}
- PPG increments (meal test)
- 1,5-anhydroglucitol
- IG measurements (CGM)

Key safety assessments

- Number of treatment emergent hypoglycaemic episodes
- Number of adverse events

Trial products

• Faster-acting insulin aspart, 100 U/mL solution for subcutaneous (s.c.) infusion provided in 10 mL vial (Investigation Medicinal Product (IMP)– blinded)

Protocol		Date:	04 February 2016	Novo Nordisk
Trial ID: NN1218-3854	CONFIDENTIAL	Version:	4.0	
UTN: U1111-1118-2480	CONFIDENTIAL	Status:	Final	
EudraCT no.: 2010-024054-11		Page:	15 of 149	

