In a therapeutic confirmatory basal-bolus trial in adult Subjects with T1DM, faster-acting insulin aspart taken with the meal effectively improved glycaemic control and the reduction in HbA_{1c} was statistically significantly larger than with NovoRapid[®]. Mealtime faster-acting insulin aspart provided superior PPG control compared to NovoRapid[®]. No statistically significant difference was seen in overall rate of severe or blood glucose (BG) confirmed hypoglycaemic episodes between mealtime faster-acting insulin aspart and NovoRapid[®]. The rate during the first 1 hour after start of a meal, constituting a small fraction of all severe or BG confirmed hypoglycaemic episodes was statistically significantly higher for faster-acting insulin aspart compared to NovoRapid[®]. The overall safety profile for faster aspart and NovoRapid[®] was similar and as expected for insulin aspart.

In a 6-week confirmatory pump compatibility trial, no microscopically confirmed episodes of infusion set occlusions (primary endpoint) were observed with either faster-acting insulin aspart or NovoRapid[®] in adult Subjects with type 1 diabetes⁷.

In this trial, the safety profile of faster-acting insulin aspart is expected to be similar to that of NovoRapid[®]. The insulin aspart molecule has a well-known safety profile based on more than 15 years of clinical experience. Compared to NovoRapid[®], faster-acting insulin aspart contains excipients which results in a faster initial absorption of insulin aspart following s.c. injection. The added excipients are included in the Food and Drug Administration's (FDA) list for approved drug

Protocol	Date:	04 February 2016	Novo Nordisk
Trial ID: NN1218-3854	Version:	4.0	

 Trial ID: NN1218-3854
 CONFIDENTIAL
 Version: 4.0

 UTN: U1111-1118-2480
 Status: Final

 EudraCT no.: 2010-024054-11
 Page: 22 of 149

products for injections and no toxicological concerns have been predicted for s.c. use in humans at the proposed concentrations.

For further details, please refer to the current version of the faster-acting insulin aspart Investigator's Brochure (IB)⁷ and any updates hereto.

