5.3 Treatment of Subjects

At the start of the run-in period (Visit 2), Subjects will remain on their pre-trial insulin treatment. At randomisation (Visit 6), Subjects will be switched from their current insulin treatment to either faster-acting insulin aspart or NovoRapid[®] in a 1U:1U manner, keeping the current insulin delivery parameters in the pump. After the transfer to trial insulin treatment the insulin pump delivery parameters should be reviewed with regards to the need for adjustments. During the run-in period (Visit 2 to Visit 6), the basal rates and Bolus Wizard[®] should not be adjusted unless indicated for safety reasons.

In the treatment period starting at randomisation (Visit 6), the Investigators must strive to achieve a glycaemic target of fasting and pre-prandial BG between 4.0-6.0 mmol/L [71-108 mg/dL] in a treat-to-target fashion based on frequent SMPG profiles and safety. No maximum dose of insulin is specified. All Subjects will perform at least 4-point SMPG profiles on a daily basis, in accordance with section 8.3.2.2, throughout the trial. Guideline documents for the management of Insulin Pump Therapy will be provided both to the Investigators and the Subjects 20.21.

The dose adjustments must be done based on SMPG values only. No other anti-diabetic medication except the current insulin treatment is allowed during the trial after start of run-in period (Visit 2) until randomisation (Visit 6). No other insulin products except the trial medication are allowed from start of the randomisation (Visit 6) until end of treatment (Visit 22).

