8.3.3.1 Hypoglycaemic episodes

Plasma glucose should always be measured and recorded by the Subject in the diary, when a hypoglycaemic episode is suspected.

 Trial ID: NN1218-3854
 CONFIDENTIAL
 Version: 4.0

 UTN: U1111-1118-2480
 Status: Final Page: 59 of 149

All plasma glucose values:

- $\leq 3.9 \text{ mmol/L} [70 \text{ mg/dL}] \text{ or}$
- > 3.9 mmol/L [70 mg/dL] occurring in conjunction with hypoglycaemic symptoms

should be reported in the diary according to the instructions below throughout the trial from Visit 2 to Visit 23.

Upon onset of a hypoglycaemic episode the Subject is recommended to measure plasma glucose every 15 minutes until the SMPG value is > 3.9 mmol/L (70 mg/dL) or symptoms have been resolved in accordance to current guidelines²⁹.

A SMPG value \leq 3.9 mmol/L (70 mg/dL) or hypoglycaemic symptoms must trigger a Hypoglycaemic Episode form to be completed by the Subjects in the diary. Repeated SMPG measurements and/or symptoms will per default be considered as one hypoglycaemic episode until a succeeding SMPG value is > 3.9 mmol/L (70 mg/dL) and/ or symptoms have been resolved. One Hypoglycaemic Episode form is to cover these measurements and/or symptoms. However, each Hypoglycaemic Episode form will cover a period of maximum 60 minutes after onset of a hypoglycaemic episode.

In case of several low SMPG values within the 60 minutes interval, the lowest value is the one that will be reported as the SMPG value for the hypoglycaemic episode but the start time of the episode will remain as the time for the first SMPG value and/or symptom.

If a new low SMPG value is measured or the Subject still has symptoms more than 60 minutes after the first reported low SMPG value and/or symptom it is considered as a new hypoglycaemic episode and a new hypoglycaemic episode form is to be filled in.

Information on the hypoglycaemic episode will be collected partly in Subject's diary (please refer to ^A in below bulleted text) and partly recorded by the pump automatically (please refer to ^B in below text) The Investigator or designated site personnel must complete the Hypoglycaemic Episode form in the eCRF for each hypoglycaemic episode by collecting relevant data from the Subject's diary and from the CareLink Clinical Reports. If for any reason the required data is not present in CareLink Clinical the Subject's diary data can be considered as the source data.

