Step 4 in the hierarchical testing procedure is to confirm superiority of change from baseline in 1,5-anhydroglucitol 16 weeks after randomisation with fast-acting insulin aspart compared to NovoRapid[®].

The change from baseline in 1,5-anhydroglucitol will be analysed using a model similar to 1), but with baseline 1,5-anhydroglucitol as a covariate.

Superiority will be confirmed if the upper boundary of the two-sided 95% confidence interval of the mean treatment difference (fast-acting insulin aspart minus NovoRapid[®]) is below 0.

Change from baseline of time spent in low IG (≤ 3.9 mmol/L [70 mg/dL]) during CGM 16 weeks after randomisation (Step 5)

The time spent in low IG is defined for each Subject at each CGM period as the accumulated time in hours spent below or equal to 3.9 mmol/L [70 mg/dL] from the first valid sensor value divided by the actual duration of the profile. To report the endpoint in minutes per 24 hours the ratio is multiplied by 1440.

Step 5 of the hierarchical testing procedure is to confirm superiority of change from baseline of time spent in low IG (≤ 3.9 mmol/L [70 mg/dL]) during CGM 16 weeks after randomisation with fast-acting insulin aspart compared to NovoRapid[®].

The change from baseline of time spent in low IG (≤ 3.9 mmol/L [70 mg/dL]) will be analysed with a model similar to 1), but with the corresponding baseline value as covariate.

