Data on-treatment emergent hypoglycaemic episodes are presented in terms of the number of Subjects with at least one event (N), the percentage of Subjects with at least one event (%), the number of events (E) and the event rate per 100 years of exposure (R). Separate summaries are made by severity considering all episodes, nocturnal and daytime episodes using Novo Nordisk and ADA classified episodes. All episodes will also be summarised by category, including summaries in relation to time since start of meal, as occurring within the following time intervals:

- During first 1, 2 and 4 hours after the start of the meal
- Between 1 (exclusive) to 2 hours (inclusive) after start of meal
- Between 2 (exclusive) to 3 hours (inclusive) after start of meal
- Between 3 (exclusive) to 4 hours (inclusive) after start of meal
- Between 2 (exclusive) to 4 hours (inclusive) after start of meal

Non-treatment emergent hypoglycaemic episodes will be listed.

The number of treatment emergent severe or BG confirmed hypoglycaemic episodes (all, daytime, nocturnal, 1 hour, 2 hour, 4 hour, 1 (exclusive) to 2 hours (inclusive), 2 (exclusive) to 3 hours (inclusive), 3 (exclusive) to 4 hours (inclusive), and 2 (exclusive) to 4 hours (inclusive) after start of the meal) will be analysed based on the FAS using a negative binomial regression model with a log-link function and the logarithm of the time period in which a hypoglycaemic episode is considered

treatment emergent as offset. The model will include treatment, strata (two levels based on use of own CGM or not), previous insulin use (three levels: NovoRapid[®], Apidra[®], Humalog[®]), and region as factors. To the extent where data allow, separate analyses will be performed for all severe episodes.

Number of unexplained episodes of hyperglycaemia (confirmed by SMPG)

The number of unexplained episodes of hyperglycaemia will be summarised in a frequency table. Unexplained hyperglycaemia is defined as a confirmed PG value ≥ 16.7 mmol/L (300 mg/dL) and is unexplained (i.e. no apparent medical, dietary, insulin dosage or pump failure reason). The percentage of Subjects with unexplained hyperglycaemia will be presented.

Unexplained hyperglycaemic episodes will be defined as treatment emergent if the onset of the episode occurs on or after the first day of IMP administration after randomisation and no later than one day after the last day on IMP.

Physical examination

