The physical examination parameters (head, ears, eyes, nose, throat, neck, respiratory system, cardiovascular system, gastrointestinal system incl. mouth, musculoskeletal system, central and peripheral nervous system, skin), and their change from baseline, will be summarised descriptively. All findings will be listed.

Electrocardiogram

Electrocardiogram (ECG) findings will be summarised descriptively including summaries of the change from screening. Change from screening will be summarised as normal/abnormal not clinically significant/abnormal clinically significant categorisation in shift tables.

Vital signs (blood pressure, pulse)

Vital signs include diastolic blood pressure, systolic blood pressure and pulse. The measurements will be summarised descriptively using both the actual values as mean change.

Fundus photography/fundoscopy

Fundus photography/fundoscopy findings and the change from screening will be summarised descriptively.

Clinical laboratory assessments

Change from baseline 16 weeks after randomisation in central laboratory assessments:

- Haematology (haemoglobin, haematocrit, erythrocytes, thrombocytes, and leucocytes)
- Biochemistry (total protein, creatinine, alanine aminotransferase (ALT), aspartate aminotransferase (AST), alkaline phosphatase (AP), sodium, potassium, albumin, and total bilirubin)
- Urinalysis (albumin/creatinine ratio, erythrocytes, protein, and ketones)

Individual laboratory values will be compared to their relevant reference range (when existing) and flagged as being below or above the range. The measurements and their change from baseline will be summarised descriptively. Change from baseline will be summarised descriptively using both the actual values and the low/normal/high categorisation in shift tables.

Change from baseline in body weight and body mass index (BMI) 16 weeks after randomisation

The measurements will be summarised descriptively using the actual values as mean change.

Change from baseline in body weight will be analysed using a statistical model similar to 1), except with the corresponding baseline measurement as covariate. The analysis will be based on the safety analysis set and the on-treatment observation period.

Number of change-of-infusion-sets per week during 16 weeks after randomisation

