In the statistical analysis for subjects reaching HbA_{1c} or PPG (SMPG) targets it has been clarified that subjects without an HbA_{1c} measurement or 1-hour mean PPG measurement at week 16 will be handled as non-responders in the on-treatment observation period analysis.

Change from baseline has been removed for fluctuation in the 7-7-9-point SMPG profile as it is analysed logarithmically transformed and change from baseline values could be negative.

CGM endpoints

Percentage of time spent with IG ≤ 3.9 mmol/L [70 mg/dL] has been added to align with the thresholds for IG for the endpoints incidence of episodes.

The percentage of time spent with IG > 13.9 mmol/L [250 mg/dL] and incidence of episodes with IG > 13.9 mmol/L [250 mg/dL] has been added to further evaluate the effect and safety of fast-acting insulin aspart.

It has been clarified the variation in the IG profile will be presented by the fluctuation.

The change from baseline in $\Delta\text{AUC}_{\text{IG},0-15\text{min}}$, $\Delta\text{AUC}_{\text{IG},0-30\text{min}}$, $\Delta\text{AUC}_{\text{IG},0-1\text{h}}$, $\Delta\text{AUC}_{\text{IG},0-2\text{h}}$ and $\Delta\text{AUC}_{\text{IG},0-4\text{h}}$ are added to further evaluate the effect and safety of fast-acting insulin aspart.

It has been clarified that the endpoints related to CGM and meal test derived as AUCs will be weighted by the duration.

Adverse events

For adverse events summaries by relation to device has been change to relation to technical complaint to align with what is reported on the case report forms. Summaries for AEs leading to withdrawal from trial have been added to further investigate the safety of fast -acting insulin aspart.

Hypoglycaemic episodes

The endpoints treatment emergent hypoglycaemic episodes occurring within 1 (exclusive) to 2 hours (inclusive), 2 (exclusive) to 3 hours (inclusive), 3 (exclusive) to 4 hours (inclusive) after start of the meal has been added to further investigate the safety of fast-acting insulin aspart.

It has been clarified that separate statistical analysis will only be for all severe hypoglycaemic episodes as the number is expected to be very low.

Unexplained hyperglycaemic episodes

The treatment emergent definition for unexplained hyperglycaemic episodes has been clarified.

Assessments not collected at baseline

ECG and fundus photography/fundoscopy is not collected at baseline, hence change from screening will be summarised for these endpoints instead.

4 References

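### The hypoglycaemia rate models omit each subject's run-in episode rate, which the trial already collects, and so give up some precision in the frequent categories

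*SAP*

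**What the plan says.** SAP section 2.4.2.2 (and Protocol section 17.4.2.2) compares the arms on severe or BG confirmed episodes by negative binomial regression on the FAS. The link is log and the offset is log treatment-emergent time. On covariates the SAP states: "The model will include treatment, strata (two levels based on use of own CGM or not), previous insulin use", followed by region. Nothing measured on the subject's own hypoglycaemia enters the model.

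Protocol section 8.3.3.1 shows that the information exists. Low glucose values and symptomatic episodes "should be reported in the diary according to the instructions below throughout the trial from Visit 2 to Visit 23". Visit 2 opens the four-week run-in. The trial meter is issued then, and daily 4-point profiles run from Visit 2 to Visit 22 (Protocol section 8.3.2.2). The episode form also records the last main meal.

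Elsewhere the SAP does use baseline values. Body weight, the other safety endpoint with a comparative model, is analysed "using a statistical model similar to 1), except with the corresponding baseline measurement as covariate". Time in low interstitial glucose "will be analysed with a model similar to 1), but with the corresponding baseline value as covariate" (SAP section 2.4.1), and that baseline comes from CGM worn during the run-in (Protocol section 8.5.1.2).

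The general considerations in both documents restrict data from before Visit 6 to descriptive summaries.

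**The concern.** Protocol section 1 lists "Number of treatment emergent hypoglycaemic episodes" as one of two key safety assessments. Subjects differ widely in how prone they are to hypoglycaemia. In a negative binomial model that spread appears as dispersion, and when episodes are frequent the dispersion dominates the standard error of the rate ratio. A pre-randomisation measure of the same behaviour can explain part of it, and it also corrects any chance imbalance in hypoglycaemia-prone subjects. Leaving it out biases nothing, but it gives a wider interval than the data allow, and in a safety comparison the interval's width decides how large an excess risk can be excluded.

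The benefit is confined to the frequent categories. In the earlier trial the first hour after a meal was described as "constituting a small fraction of all severe or BG confirmed hypoglycaemic episodes" (Protocol section 3.1.2). SAP section 3 says that "separate statistical analysis will only be for all severe hypoglycaemic episodes as the number is expected to be very low".

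**Working it through.** **1. The plan's own figure.** No precision or power is stated for hypoglycaemia. The sample size comes from Step 2 of the hierarchy: 0.9 / (3.4 × √(2/225)) = 2.81, and a two-sided 5% t-test on 448 df then gives 80.0% power, as the plan states. I therefore take 225 per arm as given.

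**2. Where the standard error comes from.** With n per arm, mean treatment-period count μ = rate × 16/52 and dispersion k, the planned model has approximately

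SE(log rate ratio) = √[(2/n) × (1/μ + k)].

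A run-in covariate can reduce k but not 1/μ. It is also noisy when the expected run-in count, rate × 4/52, is small. Rates (episodes per patient-year) and k are assumptions.

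| Rate | k | μ | 1/μ | SE by formula | SE simulated | Share due to k, k/(1/μ + k) | Run-in count |
|---|---|---|---|---|---|---|---|
| 40 | 0.8 | 12.31 | 0.081 | 0.0885 | 0.0881–0.0886 | 91% | 3.1 |
| 20 | 0.8 | 6.15 | 0.163 | 0.0925 | 0.0921–0.0924 | 83% | 1.5 |
| 4 | 1.5 | 1.23 | 0.813 | 0.143 | 0.1430–0.1435 | 65% | 0.31 |
| 1 | 2.0 | 0.31 | 3.25 | 0.216 | 0.2157–0.2165 | 38% | 0.08 |
| 0.2 | 4.0 | 0.062 | 16.25 | 0.424 | 0.438–0.442 | 20% | 0.015 |

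The gain must therefore fade as events become rare.

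**3. Gain in frequent categories.** Simulation: 225 per arm, 28-day run-in, 113 days of treatment-emergent time (112 + 1), true rate ratio 1, log-normal subject frailty. The model has a log-time offset, treatment and one binary stratum, fitted with and without the run-in rate; 1000 trials per cell (800 at correlation 0.2). Entries are adjusted SE divided by unadjusted SE.

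| Rate, frailty variance | Corr. 0.2 | 0.4 | 0.6 | 0.8 |
|---|---|---|---|---|
| 20, 0.6 | 0.995 | 0.980 | 0.955 | 0.913 |
| 20, 1.2 | 0.993 | 0.973 | 0.937 | 0.878 |
| 40, 0.6 | 0.992 | 0.969 | 0.927 | 0.863 |
| 40, 1.2 | 0.991 | 0.962 | 0.910 | 0.824 |

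At correlation 0.6 and variance 0.6 to 1.2, the extreme ratios 0.955 and 0.910 correspond to 1/0.955² = 1.10 and 1/0.910² = 1.21, the information from 10–21% more subjects. At 0.2 the same sum gives 1/0.995² = 1.01 to 1/0.991² = 1.02. A separate rerun agreed within 0.01 for the frequent categories (for example 0.958 against 0.955, and 0.826 against 0.824).

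**4. Gain in sparse categories.** Covariate: the overall run-in rate, at 20 per patient-year; frailty variance 1.0.

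| Outcome rate | Corr. 0.4 | 0.6 | 0.8 |
|---|---|---|---|
| 5 | 0.983 | 0.959 | 0.920 |
| 2 | 0.989 | 0.974 | 0.950 |
| 1 | 0.993 | 0.984 | 0.968 |
| 0.3 | 0.998 | 0.995 | 0.990 |

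Using the category's own run-in count does worse: 0.993, 0.981, 0.965 at 5 per year and 0.998, 0.994, 0.988 at 2. The overall rate is the better covariate.

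**5. Second simulation.** Gamma frailties linked by a Gaussian copula, with the k values of step 2, up to 300 trials per cell and the category's own run-in count. SE ratios at correlation 0.5, 0.7, 0.9 were 0.94, 0.88, 0.76 at 40 per year; 0.96, 0.91, 0.84 at 20; 0.98, 0.96, 0.93 at 4; and 0.98 to 1.00 at 1 per year or less. At 4 per year the empirical spread of the estimates fell less than the model SE (for example 0.1416 to 0.1402 at 0.9), so the gain there should not be relied on.

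**6. Validity.** In the first simulation the mean log rate ratio stayed within 0.01 of zero in every cell, with and without the covariate. In the second, the planned model's two-sided error in the frequent scenarios was 0.04 to 0.06. The adjusted model's was 0.037 to 0.060, apart from one cell at 0.083 (40 per year, correlation 0.7). With 300 trials the Monte Carlo error is √(0.05 × 0.95/300) = 0.013, and the adjacent correlations gave 0.050, so I do not read this as a pattern.

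**The case against.** The strongest reply is that this is preference, not defect. The endpoint is supportive, outside the hierarchy, and has no margin or power claim. The decisive input, the run-in/treatment correlation, is unknown and may be low: in the run-in, subjects stay on pre-trial insulin and pump settings "should not be adjusted unless indicated for safety reasons" (Protocol section 5.3), whereas afterwards insulin is switched and titrated to target. At a correlation of 0.2–0.4 the gain is only 1–4%. The simulations also omit previous insulin use, region and dropout, and those factors might absorb part of the gain. All of this stands, and it keeps the point minor. A low correlation shrinks the benefit but cannot bias a randomised comparison.

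It can also be said that body weight and time in low glucose are change scores, which a count is not. That is true, but the SAP also adjusts its HbA1c and PPG responder models for baseline, and these are not change scores.

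The rule on pre-randomisation data is followed by the planned model. HbA1c and body weight are measured at Visit 6 itself, so only the CGM baseline is a real precedent for using run-in data. The sentence therefore needs a clarifying clause.

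Finally, the earlier trial's signal lay in the first hour after meals, where the covariate helps little. That stands too. The overall rate still has to be estimated, and it is the category where precision can be gained cheaply.

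**Conclusion.** The point holds as an efficiency suggestion. The planned models are valid, and with no treatment-by-covariate interaction the log link makes the rate ratio collapsible, so the covariate leaves the target unchanged. What is lost is width: about 1% of the interval on the log scale at correlation 0.2, rising to 9–18% at 0.8, for 20–40 episodes per patient-year and 225 per arm. At correlations of 0.4–0.8 with the overall run-in rate, the narrowing is 2–8% at 5 per year, 1–5% at 2, 1–3% at 1 and 0–1% at 0.3. These figures depend on assumed rates, dispersion and correlation, none of which the documents supply. No conclusion of the trial is shown to turn on it.

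**What to change.** Before unblinding, add log((run-in severe or BG confirmed episodes + 0.5) / run-in exposure time, Visit 2 to Visit 6) as a covariate to the negative binomial models for all and daytime episodes. Extend it to nocturnal episodes and the 2 h, 4 h and 2–4 h meal windows under a count rule fixed in advance, for example a blinded pooled rate of at least 5 per patient-year. Leave the severe-episode model and the sparse meal windows as planned, and report the currently planned model as supplementary output.

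State in the SAP that limiting pre-randomisation data to descriptive summaries does not exclude baseline covariates. The same sentence stands in Protocol section 17, so record the change in SAP section 3.

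The cost is one covariate, one clause and one supplementary table; no new data are needed.
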